### 2.3. Description of participants

#### **Purpose:**

To determine distribution of baseline characteristic within study sample compared to target population (i.e., pregnant and breastfeeding women in Cape Town).

#### **Methods/Approach:**

Construct “Table 1” describing the baseline characteristics of each intervention group including:

- (1) Demographic characteristics (e.g., age, socioeconomic status, ethnicity, gestational age at baseline, number of children, knowledge of PrEP, relationship status, risk factors)
- (2) Baseline exposure characteristics (e.g., PrEP initiation)
- (3) Baseline disease characteristics (i.e., STI results)
- (4) Baseline values of primary and/or secondary outcome variables (note, this may be a separate table)

### 2.4. Primary analysis/results

#### **Purpose:**

To measure the distribution of women across the PrEP cascade including: initiation, continuation and persistence

#### **Methods/Approach:**

- (1) **Primary outcome:** See **Table 1** for precise definitions of (1) PrEP initiation, (2) PrEP continuation, (3) PrEP persistence-subjective, and (4) PrEP persistence-objective
- (2) **Primary analysis:** Describe each outcome listed above via cumulative incidences at fixed intervals (e.g., cumulative PrEP initiation by delivery) and incidence densities over time. The general statistical approaches to these outcomes are analogous; data will be described graphically, including product-limit graphs, with preliminary analyses based on standard approaches for rates and proportions.
  - a. **PrEP initiation** will be modelled using a probit model (preferred to estimate risk factors for common outcomes) with individual-level covariates as fixed effects.
  - b. **PrEP continuation** will be examined using similar approaches; in addition, we will use time-to-event methods to estimate factors associated with time to loss (non-continuation) among women having initiated PrEP.
  - c. **PrEP persistence** will be modelled using mixed effects probit models as above and generalized estimating equations to examine the marginal effect of individual-level covariates on persistence during the study.
    - a. **Sub-group analysis:** we will analyze the primary outcomes by sub-groups including age (<25 and  $\geq$ 25 years), STI diagnosis, relationship status, pregnant/postpartum

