#### **4. Study population**

Study counselors will enroll consecutive eligible, consenting pregnant adolescent girls ( $\geq 16$  years) and women in ANC (n=600 women per site; N=1200 pregnant women) and follow them up for 12-months postpartum or until censorship for a mean of 18-months' follow-up.

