##### Inclusion Criteria:

- 1.  $\geq 16$  years old**
- 2. confirmed HIV-negative (confirmed with a 4th generation antigen HIV test)**,
- 3. Intend on giving birth in the MOU facility**
- 4. confirmed to be pregnant**
- 5. without psychiatric or medical contraindications to PrEP.**

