##### Exclusion criteria:

Individuals not meeting the above criteria or meeting any of the following criteria will be excluded:

- Concurrent enrolment in another HIV-1 vaccine or prevention trial**
- Medical hospitalization in the past year, for reasons not associated with obstetric health (e.g. c-section, miscarriage, pre-eclampsia)**
- Active TB or receipt of TB treatment within the past 30 days**
- History of renal disease**
- Current clinical diagnosis of hypertension**
- Exhibiting psychotic symptoms (including hallucinations, suicidal or homicidal ideations, or violent behaviour)**
- Currently or history of taking an anti-psychotic medication (such as for treatment of bipolar disorder, schizophrenia, or postpartum psychosis following a previous pregnancy)**
- Positive Hepatitis B surface antigen (HBsAg) test on screening**
- History of bone fracture not related to trauma**

- Any other medical, psychiatric or social condition which in the opinion of the investigators would affect the ability to consent and/or participate in the study.

Study censorship will include:

1. Seroconversion
2. Moves away
3. Transfers out of care
4. Lost to follow up (e.g. does not return for study or clinical visit for >8 weeks and study staff are unable to track the participant, or she does not want to continue in the study).

Eligible, consenting women will receive up to R250 in grocery vouchers, transportation and refreshments per visit for their time and effort in the study as well as transportation to the facility. All participants will also receive minor refreshments (e.g. sandwich and cool drink) on the day of their visit.

Procedures for the informed consent process are outlined below. Throughout, trained study staff will ensure that women are aware of their right to refuse and/or withdraw from the study at any time. In addition, study staff will emphasize that all study activities are entirely separate from routine ANC and postnatal care services received and that refusal or withdrawal from the study will have no impact on their ability to access any services provided at any public-sector health facility.

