## **Laboratory tests in all women in the cohort:**

- **STI testing:** Self-collected vaginal swab kits will be provided to all participants along with an explanation for their use. Swabs will be analyzed in the laboratory for chlamydia and gonorrhea. Results for STI testing will be provided in 2-3 weeks after analysis and participants will be called in with STI+ results for treatment and partner referrals
- **HIV testing.** As part of the standard of care, all pregnant and breastfeeding women will be tested for HIV using serial rapid HIV tests at each antenatal and postnatal care visit. In addition, PrEP-PP study staff will test for HIV using antigen and antibody HIV tests to rule out acute HIV infections.
  - **Seroconversion.** If a woman, infant or partner seroconverts at any point during the study (including antigen+, antibody+ or antibody/antigen+), they will stop PrEP immediately and be referred to the clinician on duty to initiate ART on the same day, following counseling about PMTCT, breastfeeding, disclosure, and ART adherence, per the SA National Protocols [17]. Seroconverted women will be censored from the remainder of the study and referred to the clinic to initiate ART.
  - If a woman seroconverts while on PrEP, there may be a risk of ART resistance, though research has demonstrated that the risk of ART resistance is very low [12, 13]. In the case of seroconversion, Drs [name] and [name] will follow seroconverters with the study team to evaluate if the patient achieves viral suppression within 6 months of ART start, and if not, she will be referred for specialist attention for testing for ART resistance and clinical follow-up.

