- **Measurement of use of PrEP:** Conducted through alternate definitions of the main outcomes (e.g. persistence by self-report versus persistence by pharmacy refill), compared using measures of agreement and will be analyzed as independent models to contrast estimated associations.
- **Measurement of prevention-effective execution:** Execution refers to PrEP persistence during a time when at-risk sex happens. It is calculated by: number of doses reported, or recorded/number of expected doses based on HIV risk and PrEP initiation/discontinuation
- **Prevention-effective continuation:** Prevention-effective continuation describes the duration of PrEP use during periods of HIV risk and references the absolute time of use during pregnancy and breastfeeding periods. We will adapt the methodology from previous PrEP studies in SA including FEM-PrEP to create a semi-ordinal composite persistence score from blood specimens from DBS every 2-months.  
For *Aim 1*, each outcome will be described via cumulative incidences at fixed intervals (e.g., cumulative PrEP initiation by delivery) and incidence densities over time. The general statistical approaches to these outcomes are analogous; data will be described graphically, including product-limit graphs, with preliminary analyses based on standard approaches for rates and proportions.

For *Aim 1*, we will also describe the frequency of HIV outcomes, including maternal HIV acquisition and MTCT, and any laboratory or self-reported side effects (e.g. changes in creatinine or self-reported side-effects [GI symptoms, headache, and etc.]). Analyses will include pure-count and person-time approaches; for the latter, confidence intervals will be calculated following the method of Breslow and Day. We will also describe infant outcomes over time (including birthweight, gestational age at delivery, pregnancy loss and any infant illness, hospitalization or death). While we expect the frequency of adverse HIV-related outcomes to be low, we will

describe characteristics of women who did/did not acquire HIV, and consider further analyses using the approaches outlined above.

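### Seroconversion is censored although it rules out starting PrEP and ends its use, so product-limit curves overstate cumulative initiation and, if read as the share still on PrEP, continuation

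*Combined protocol and SAP*

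**What the plan says.** **Follow-up and censoring.** Protocol section 4 plans to "follow them up for 12-months postpartum or until censorship for a mean of 18-months' follow-up". Its list headed "Study censorship will include" puts seroconversion first, beside moving away, transfer out and loss to follow-up. Protocol section 5 (laboratory tests in all women) repeats this: "Seroconverted women will be censored from the remainder of the study and referred to the clinic to initiate ART".

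**What seroconversion does to PrEP.** The same part of section 5 says of those who seroconvert that "they will stop PrEP immediately and be referred to the clinician on duty to initiate ART on the same day". Inclusion criterion 2 requires a confirmed negative HIV test, so the cascade concerns HIV-negative women only.

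**Analysis.** SAP section 1 (statistical analysis considerations) says "each outcome will be described via cumulative incidences at fixed intervals (e.g., cumulative PrEP initiation by delivery) and incidence densities over time". SAP 2.4 repeats this and adds that "data will be described graphically, including product-limit graphs"; SAP 2.5 carries the approach over to the secondary outcomes. For continuation, SAP 2.4 adds that "we will use time-to-event methods to estimate factors associated with time to loss (non-continuation) among women having initiated PrEP".

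**Informative loss.** SAP section 1 plans inverse probability of censoring weighting, complete-case analysis and multiple imputation. Neither document names a competing event or a competing-risk estimator.

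**The concern.** A product-limit estimate treats a censored woman as someone who would go on to have the event at the same rate as the women still followed. That can be defended for a woman who moves away: she may still start or stop PrEP, only unseen. It cannot be defended for a woman who has acquired HIV. If she had not started PrEP, she never will; if she was taking it, her use has ended.

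The directions follow from this:

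- **Initiation:** one minus the product-limit curve is too high.
- **Continuation, read as the share still on PrEP:** the curve is too high, because women whose use ended with infection are assumed to carry on.
- **Continuation, read as non-continuation alone:** one minus the curve slightly overstates stopping.

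Censoring weights do not help. They estimate what would happen if nobody seroconverted, whereas protocol objective 1 asks what proportion of all women offered PrEP start it. At stake are the displayed curves for primary outcomes in a setting chosen for its high HIV incidence.

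**Working it through.** **The plan's own figures.** The cascade in SAP 2.2 reproduces: 1200 × 0.60 = 720 starting; 720 × 0.75 = 540 continuing at 12 months; 540 × 0.70 = 378 adherent.

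**Inputs.** Background maternal incidence is 10.7 per 100 person-years and the risk ratio on PrEP in women is 0.57 (95% CI 0.34 to 0.94), both from protocol section 1. Assumptions: constant hazards; the risk ratio used as a rate ratio; the planned 75% and 60% used as the product-limit values; low background incidence taken as 1 to 2 per 100 person-years, because the SAP gives no figure.

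**Continuation at 12 months.** Let h be the hazard of stopping and λ the hazard of HIV on PrEP.

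- h = −ln(0.75) = 0.2877 per year; λ = 0.107 × 0.57 = 0.061 per year.
- Product-limit value: exp(−h) = 75.0%.
- On PrEP and HIV-free: exp(−(h + λ)) = 0.75 × exp(−0.061) = 70.6%. The gap is 4.4 points, or 540 against about 508 of 720 women.
- Binomial standard error: √(0.75 × 0.25 / 720) = 1.6 points, so the gap is about 2.8 standard errors.
- Non-continuation alone: h/(h + λ) × [1 − exp(−(h + λ))] = 24.3%, against 25.0% from the product-limit curve. The difference is 0.7 points, or 0.44 standard errors.

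| Incidence | λ per year | Overstatement of share on PrEP and HIV-free |
|---|---|---|
| Background 10.7, RR 0.57 | 0.061 | 4.4 points |
| Background 10.7, RR 0.34 to 0.94 | 0.036 to 0.101 | 2.7 to 7.2 points |
| 3 per 100 person-years on PrEP | 0.030 | 2.2 points |
| Background 2, RR 0.57 | 0.0114 | 0.9 points |
| Background 1, RR 0.57 | 0.0057 | 0.4 points |

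**Initiation.** Let b be the share starting on the day of enrolment, which the documents do not give. The later starting hazard h₁ is set so that the product-limit value is 60% at time T: h₁ = −ln(0.40/(1 − b))/T. With λ = 0.107 before starting, the competing-risk value is b + (1 − b) × h₁/(h₁ + λ) × [1 − exp(−(h₁ + λ)T)]. The standard error is √(0.6 × 0.4 / 1200) = 1.4 points.

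| Starting at enrolment (assumed) | Overstatement by delivery, T = 6 months | Overstatement by 17 months |
|---|---|---|
| 20% | 0.9 points | 2.6 points |
| 40% | 0.5 points | 1.3 points |
| 50% | 0.25 points | 0.7 points |

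Six months is the 18-month mean follow-up less 12 months postpartum. Seventeen months is an illustrative late horizon that the documents do not state. At 2 per 100 person-years, the overstatement by delivery is at most 0.25 points even if nobody starts at enrolment.

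**The case against.** **Only the graphs are tied to the product-limit method.** The primary outcomes in SAP Table 1 are simple proportions or rates per woman-time, and no estimator is named for the cumulative incidences. This stands: the tables may be unaffected. It limits the point to the curves and gives a reason to name the estimator.

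**The 4.4 points are not an error on the SAP's own endpoint.** Continuation is defined by visit attendance, and for non-continuation the error is 0.7 points at the cited rates. This stands too. The larger figure applies only when the curve is read as the share still taking PrEP, which is a natural reading of a cascade graph but not the SAP's definition.

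**The inputs are unfavourable.** The protocol gives 10.7 per 100 person-years as an upper figure, while the SAP expects few HIV events. PrEP is offered at the enrolment visit, and the SAP's example horizon is delivery. These affect the size, not the direction.

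**Two stronger readings are tempting and are not supported.**

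- A reader might infer that women who seroconvert go uncounted. They do not: SAP Table 1 and section 2.5 report maternal HIV acquisition, and section 2.6 tabulates reasons for ending treatment.
- A reader might infer that the Aim 3 model receives biased inputs. That model simulates maternal infection itself and takes a PrEP discontinuation rate. A rate with seroconversion censored is the cause-specific quantity it needs; a share already reduced by infection would risk counting infection twice.

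**The completer rule.** If SAP 2.4's restriction to women who complete 12 months postpartum were applied to the curves, women who seroconvert would leave the dataset and this mechanism would not arise. That is a separate selection problem and not a remedy. Separate analyses of PrEP stoppage are also planned, but the SAP does not say that they count seroconversion.

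**Conclusion.** The point holds for the product-limit displays. The direction is certain, because an event that makes starting impossible, or ends use, is handled as ordinary censoring. The size is conditional. It reaches several points for the share still on PrEP at the incidence the protocol cites, and falls below 1 point at a background of 1 to 2 per 100 person-years with RR 0.57. For initiation it is under 1 point by delivery when at least 20% start at enrolment, and larger at later horizons. All figures rest on constant hazards and, for initiation, on an assumed share starting at enrolment. The documents do not support saying that the tabulated results are wrong. The change is worth making before analysis: it gives the right curve at any incidence and needs only a change of wording.

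**What to change.** In SAP 2.4 and 2.5:

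1. Show initiation and continuation with Aalen-Johansen cumulative incidence, and name the same estimator for the tabulated cumulative incidences.
2. Make seroconversion its own state. For initiation: started, seroconverted before starting, neither. For continuation: on PrEP, stopped or lost, seroconverted.
3. State that seroconversion ends follow-up of the cascade but is analysed as an outcome state. Keep censoring for the administrative end of follow-up and for moves and transfers.
4. Keep cause-specific hazard models for predictors, and use the cause-specific discontinuation rate for Aim 3.

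The cost is SAP wording and a standard software option. No new data are needed, because HIV is tested at every study visit. The displayed initiation and on-PrEP curves will be slightly less favourable.

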#### **Missing data:**

Primary persistence analyses will use objective measures (TDF-DP from DBS) taken on all those who enrolled and initiated PrEP; subsidiary analyses will consider (i) other persistence measures and (ii) multiple imputation for missing persistence data. Specify any sensitivity analyses. Specify how the impact of missing data on the primary results will be interpreted.

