**Table 1. Study measures for PrEP-PP for AIM 1**

Primary Outcomes	Measurement	Source	Frequency
PrEP initiation	# of women who initiate PrEP over time / total # of women in active cohort = proportion of women who initiate PrEP	Electronic provider log (REDCap)	Quarterly
PrEP continuation	# of women on PrEP who return for study visits (do not miss more than 1 visit) / total # of women in active cohort who are prescribed PrEP= proportion of women on PrEP who continue in PrEP study	Electronic provider log (REDCap)	Quarterly
PrEP persistence (subjective)	# of women reporting taking PrEP in $\geq 5$ out of last 7 days or $\geq 25$ out of last 30 days (self-reported)/ total woman-time on PrEP in active cohort = PrEP persistence rate (subjective)	Electronic provider log (REDCap)	Quarterly
PrEP persistence (objective)	# of women taking PrEP who have $\geq 600$ fmol/punch (~7 doses/week) from DBS TDF-DP at 3rd trimester, delivery, and 6 weeks postpartum (and during sexual risk periods during that time) / total woman-time on PrEP in active cohort = PrEP persistence rate (objective)	Lab analysis of TDF-DP measures	Yearly and end of study
Secondary Outcomes			
Prevention effective persistence	4. # of women reporting adherence to PrEP (as per PrEP persistence subjective measure)/ total woman-time reporting sexual activity in past 30 days	Electronic provider log (REDCap)	Quarterly
	5. # of women having TDF-DP in DBS (as per PrEP persistence objective measure)/ total woman-time reporting sexual activity in past 30 days	Lab analysis of TDF-DP measures	Yearly and end of study

Prevention effective continuation	# of women who don't miss any PrEP study visits/ total woman time reporting sexual activity in prior visit	Electronic provider log (REDCap)	Quarterly
Predictors of attrition at key steps in the PrEP cascade	Individual, pill/study and disease specific predictors of PrEP initiation, continuation and persistence	Study CRFs and in-depth interviews (month 7 and12) (mixed methods)	End of study
Healthcare provider attitudes and knowledge about PrEP in pregnancy	Provider knowledge about PrEP and barriers/facilitators to PrEP prescription in ante and postnatal care	In-depth interviews	Year 1 of study
HIV outcomes	HIV testing data: HIV-uninfected, HIV incidence in mother and child (if mother seroconverts) compared by PrEP use/non-use	Electronic provider log (REDCap)	End of study

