#### 4. Table and Figure Templates

Outline tables and figures that will be produced for the analysis. This will include all analyses. Tables and figures for the paper will be constructed separately.

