**Table 2. Continuation, persistence and outcomes in those on PrEP (n=XXX)**

	On PrEP (n=XXX)		Change from last quarter
	n	%	
Returned for 1 month visit			
Persistence (self reported taking PrEP 5+ days of last 7 days)			
Persistence (self reported taking PrEP 25+ days of last 30 days)			
Returned for 3 month visit			
Persistence (self reported taking PrEP 5+ days of last 7 days)			
Persistence (self reported taking PrEP 25+ days of last 30 days)			
Returned for 6 month visit			

Persistence (self reported taking PrEP 5+ days of last 7 days)				
Persistence (self reported taking PrEP 25+ days of last 30 days)				
Returned for 9 month visit				
Persistence (self reported taking PrEP 5+ days of last 7 days)				
Persistence (self reported taking PrEP 25+ days of last 30 days)				
Returned for 12 month visit				
Persistence (self reported taking PrEP 5+ days of last 7 days)				
Persistence (self reported taking PrEP 25+ days of last 30 days)				
Returned for 15 month visit				
Persistence (self reported taking PrEP 5+ days of last 7 days)				
Persistence (self reported taking PrEP 25+ days of last 30 days)				
Returned for 18 month visit				
Persistence (self reported taking PrEP 5+ days of last 7 days)				
Persistence (self reported taking PrEP 25+ days of last 30 days)				
Continuation on PrEP at v3 (defined as not missing >1 Study visit in those on PrEP)				
Continuation on PrEP at v4				
Continuation on PrEP at v5				
Continuation on PrEP at v6				
Continuation on PrEP at v7				

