### Part 3: PrEP persistence and side effects

#### PrEP persistence and side effects at the refill visit (v1.1) and V2+

	V1.1	V2	V3	V4	V5
Taken PrEP in the last 30 days	N, %				
Yes					
No					
Had symptoms or side effects while on PrEP					
Yes					
No					

In the last 30 days, on how many days did you miss at least one dose of any of your PrEP					
Never missed (0 days)					
1 - 5 days					
6-10 days					
11-20 days					
>20 days					
In the last 7 days, on how many days did you miss at least one dose					
Never missed (0 days)					
1-3					
4-7					

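### The SAP makes DBS drug level the primary persistence analysis but also lists self-report as an equal primary outcome and joins the two with "or", so the deciding measure is not fixed

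*Combined protocol and SAP*

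**What the plan says.** Two statements rank the measures. SAP section 2.4, under Missing data, says "Primary persistence analyses will use objective measures (TDF-DP from DBS) taken on all those who enrolled and initiated PrEP" and continues that "subsidiary analyses will consider (i) other persistence measures and (ii) multiple imputation for missing persistence data". The SAP's statistical considerations for Aims 1 and 2 repeat this, and section 6 of the protocol says the same of adherence.

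Other places do not rank them:

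- SAP section 2.4, Methods/Approach item (1), includes among the primary outcomes "3) PrEP persistence-subjective, and (4) PrEP persistence-objective".
- SAP Table 1 (study measures) has both under Primary Outcomes. One row ends "total woman-time on PrEP in active cohort = PrEP persistence rate (subjective") and the next ends "total woman-time on PrEP in active cohort = PrEP persistence rate (objective").
- Protocol Table 2 likewise lists subjective and objective adherence as two primary outcomes.
- The SAP's Aim 1 objectives and item 3 of its study measures define persistence as either self-report rule *or* at least 600 fmol/punch of TDF-DP.

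The Interpretation paragraph of SAP section 2.4, where a rule for conflicting results belongs, still holds unfilled template instructions on this point.

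The table shells in SAP section 4 are introduced with "This will include all analyses". The shell on continuation and persistence has rows such as "Persistence (self reported taking PrEP 5+ days of last 7 days"), and Part 3 asks "In the last 7 days, on how many days did you miss at least one dose". No shell has a DBS or TDF-DP row.

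**The concern.** Persistence is the last step of the cascade that the study exists to describe, and the protocol uses the cohort's results as inputs to the Aim 3 model. If three parts of the plan support three versions of the outcome (DBS alone, two equal primaries, or a combined definition), the choice between them can be made after the results are known, and each version can be defended from the text.

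The versions are not interchangeable. The self-report rule and the DBS threshold aim at different dosing levels, so they can disagree even when every woman reports accurately. The plan itself intends to study their agreement, so it allows for them to differ, but it does not say what follows for the persistence result when they do.

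**Working it through.** **The plan's own figures.** 1200 × 0.60 = 720 initiators; 720 × 0.75 = 540 retained; 540 × 0.70 = 378 adherent. This reproduces the stated 378. The sample-size text ties that number to TDF-DP, which supports reading DBS as the intended primary measure.

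**The passages side by side.**

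| Place | Standing of DBS | Standing of self-report |
|---|---|---|
| SAP, statistical considerations for Aims 1 and 2; SAP 2.4 Missing data | primary | subsidiary |
| Protocol section 6, statistical analysis considerations | primary | subsidiary |
| SAP Table 1; SAP 2.4 Methods/Approach (1) | primary | primary |
| Protocol Table 2 | primary | primary |
| SAP Aim 1 objectives; SAP Study measures, item 3 | sufficient alone | sufficient alone |

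**Dosing level each measure targets**, as a share of daily doses:

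- Self-report, 7-day rule: 5/7 = 0.714.
- Self-report, 30-day rule: 25/30 = 0.833.
- DBS threshold, which SAP Table 1 labels as about 7 doses a week: 7/7 = 1.00.

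A woman who takes 5 doses every week and says so meets the first rule but is below the dosing level that the DBS threshold is said to represent.

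**Effect of the *or*.** Let S be persistent by self-report and D persistent by DBS. Then P(S or D) = P(D) + P(S and not D), which cannot be lower than P(D). The excess over the DBS figure is exactly the share of women who qualify on self-report alone. The documents give no value for that share. As a scale only, 1 percentage point of the 720 planned initiators is 0.01 × 720 = 7.2 women.

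**Table shells.** Of all the shells in SAP section 4, only the continuation-and-persistence shell and Part 3 report persistence. Both use self-report only.

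**Part 3 bins.** At least 5 of 7 days taken means at most 2 missed. The bins are 0, 1–3 and 4–7 missed days:

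- 0 missed: meets the rule.
- 1–3 missed: mixed. 1 or 2 missed (6 or 5 taken) meets it; 3 missed (4 taken) does not.
- 4–7 missed: does not meet it.

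From this table the 5-of-7 share can only be bounded, between the share with 0 missed and the share with 0–3 missed. The 30-day bins do fit their rule: 25 of 30 taken means at most 5 missed, and the bins break between 5 and 6.

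**The case against.** The strongest reply is that the hierarchy is already stated, twice in the SAP and once in the protocol, and that the power statement is tied to TDF-DP. On that reading only a labelling conflict in the outcome tables remains. This stands as evidence of intent. It does not remove the conflict, because section 2.4 sends the reader to Table 1 for the precise outcome definitions, and Table 1 does not rank the measures. Nor does it deal with the *or* definitions.

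A reader might infer from the shells that the trial means to headline self-report. The documents do not support that. Section 4 adds that tables for the paper will be built apart from these shells. The shells are incomplete in other respects too, with no rows for prevention-effective persistence or infant growth. DBS is scheduled for yearly and end-of-study analysis, which explains its absence from tables built around quarterly change and periodic reporting. It does not explain why there is no final DBS shell in a set said to cover all analyses.

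A reader might also infer that the plan predicts over-reporting. It does not: it sets out to measure reporting error in either direction. The point does not depend on the direction.

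Finally, the Part 3 bins might be read as misclassifying women. They do not. Part 3 belongs to the monthly and quarterly report templates and only tabulates missed days. The continuation-and-persistence shell reports the 5-of-7 rule directly, and nothing suggests that only binned data are stored.

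**Conclusion.** The contradiction holds. The plan ranks DBS first in its analysis text, gives self-report equal primary standing in its outcome lists, and elsewhere lets either measure suffice. It has no rule for disagreement, and the measures target about 71% or 83% of daily doses on one side and about 100% on the other. The measure that decides the persistence result is therefore not fixed.

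The numerical consequence cannot be derived, because the documents give no expected agreement between the measures. What can be said is that the combined definition can never give a lower figure than DBS alone. The dosing comparison takes the SAP's own label for the DBS threshold at face value.

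This is a fault of specification and should be corrected. It is not evidence that self-report was preferred. The missing DBS shell is a lesser gap, and the Part 3 bins are a minor matter of display.

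**What to change.** - Name DBS persistence, in all who initiated PrEP, as the single primary persistence outcome in the SAP's Aim 1 objectives, Study measures item 3, Table 1 and section 2.4 Methods/Approach (1).
- Replace the *or* definition with two measures reported separately. Make self-report secondary and use it for the planned agreement analysis.
- Align protocol Table 2, so that the correction does not create a new mismatch between protocol and SAP.
- Replace the template text under Interpretation in section 2.4 with a statement that DBS decides the persistence result when the measures disagree.
- Add one end-of-study DBS shell at the time points where the outcome is defined (third trimester, delivery and 6 weeks postpartum), showing the number tested and the number of initiators due. Rows in the existing month-by-month shell would not match those time points.
- Minor: re-cut the Part 3 seven-day bins to 0, 1–2 and 3–7 missed days. The 30-day bins need no change.

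The cost is wording in the SAP, one protocol table and one new shell, with no new data collection. The downside is that the headline persistence figure may be lower and must wait for the assays.
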